The maximum safety dosage of bupivicaine is 2mg/kg with a half life of 3.5 hours. This means a 70kg adult could receive 150mg (.15g). This calculation does not account for the slow release profile of DepoBupivicaine which would increase the maximum safe dose.

The DepoBupivicaine patients (Group 1) will receive an injection of 166mg of DepoBupivicaine diluted in 60mL, the On Q patients (Group 2) will receive an infiltration via an OnQ soaker catheter of 0.25% bupivicaine at 4mL/hour (ie. .01 gram/hour) and 0.25% Bupivicaine patients (Group 3) will receive 2mg/kg of 0.25% of bupivicaine.

Consent

All patients will sign an informed consent that will be presented to them during a preoperative visit with their attending surgeon.

Pre-operative Protocol

No preemptive morphine was given to patients. Patients at high risk for post-operative nausea and vomiting will be given Dexamethasone 4mg and Reglan 10 mg. Anesthesia will be given according to Table 1.

Table 1:

Induction	Propofol	
Intubation (muscle relaxation)	Succinylcholine	
Maintenacnce	Sevoflourane	
Muscle relaxation	Rocuronium	
Analgesia	Fentanyl 2-7 mcg/Kg	
Prophylactic Analgesia	Toradol 30- 60 mg	
Reversal	Glycopirolate + Neostigmine	
Anti-emetic	Zofran 4 mg	

Operative Technique

Surgeons for patients randomized to Group 1(DepoBupivicaine) will be given a schematic for injection of DepoBupivicaine. One 20 cc vial of EXPERAL (266 mg) will be diluted with 60 cc preservative-free normal sterile saline for a total volume of 80 cc. The infiltration technique for the DepoBupivicaine (See Baxter et al, and Hivelin et al) will be 20 cc of injected with a 25-gauge needle on either side of the suture line, (Figure 2 and Figure 3) injected directly into the fascia. The injections will be done in between the internal oblique and transversus abdominus muscles as determined via ultrasound.

Another 20 cc of will be injected on the outside edge of the surgical site where the sensory nerves branch up from the fascia to the skin flap. () The final 20 cc will be injected along the length of the incision where the skin will be anchored down with care to inject the product near the ileoinguinal nerve to ensure appropriate analgesic coverage. Once again, the DepoBupivicaine will be injected directly into the fascia above the muscle layer. All patients will have two closed-suction drains placed at the inferior aspect of the donor site, oriented horizontally and remote from the any infusion catheter..

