For patients assigned to the Group 2 (OnQ) the surgeons will be given an instruction sheet with specific placement of catheter (See Bulter et al). All patients in the group will have two ON-Q soaker catheters installed into the abdominal donor site before donor-site closure. The catheters will be inserted through 3-mm stab incisions in the suprapubic area and 3 cm caudal to the donor-site incision. One catheter will be placed directly in the plane between the internal oblique and the transversus abdominus (see Hebbard et al), and the second catheter will be placed subcutaneously, superficial to the anterior rectus sheath along the superior aspect of the donor site (Figure 1). At the conclusion of surgery, a 4-ml/hour infusion 0.25% Bupivicaine % solution will be delivered continuously by the continuous infusion

pump system (2 ml/hour through each catheter). All patients will have two closedsuction drains placed at the inferior aspect of the donor site, oriented horizontally and remote from the any infusion catheters.

Patients assigned to the control Group 3 (0.25 % Bupivicaine) will be given 0.25% bupivacaine without epinephrine. A dose of 2mg/kg will be given. Thus, a 80 kg patient will be given 80 cc of 0.25% Bupivacaine . The infiltration technique for the Maracine will be identical to the EXPERAL injection whereby 20 cc of will injected with a 25-gauge needle on either side of the suture line (Figure 2 and Figure 3) directly into the fascia above the muscle layer. The injections will be done in between internal oblique and transversus abdominus muscles as determined via ultrasound. Another 20 cc of will be injected on the outside edge of the surgical site where the sensory nerves branch up from the fascia to the skin flap (Figure 3). The final 20 cc will be injected along the length of the incision where skin will be anchored down; care will be taken to inject the product near the ileoinguinal nerve to ensure appropriate analgesic coverage (Figure 4). Once again, the 0.25% Bupivacaine will be injected directly into the fascia above the muscle layer. All patients will have two closed-suction drains placed at the inferior aspect of the donor site remote from the any infusion catheters and oriented horizontally.

[figure not shown]

Figure 1. A. OnQ catheter *in vivo* prior to closure of open abdomen (See Haller et al) B. Schematic of OnQ catheter place in a plane above the Tranversus Abdominus (TA) (see Hebbard et al)

[figure not shown]

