Figure 2. Injecting bupivacaine into fascia and along incisional lines (C) prior to closure(Baxter et al).

Figure 3 A. Open abdomen prior to closure marking site of injection of either DepoBupivicaine or 0.25 % Bupivicaine (White Arrow) B. Using ultrasound probe in vivo C. Schematic of plane between the Internal Oblique and Transversus Abdominus

Post-operative Protocol

No short-acting analgesics, such as Fentanyl, will be given post-operatively. All patients will receive a narcotic intravenously through a patient-controlled analgesia pump programmed for demand-only mode (no basal rate). The patient-controlled anesthesia will be filled with morphine or hydromorphone (if patient sensitivity to morphine). Oral narcotics will be offered when the patient's diet is advanced as tolerated, typically post-operative day 1. Patients will be encouraged to ambulate on post-operative day 1. The continuous infusion pump catheters will be removed by the surgeon when the pump is empty. Drains will be removed when output is less than 30mL in a consecutive 24 hour period.

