Our primary endpoints will be postoperative pain as measured by total postoperative morphine or hydromorphone utilization from a patient controlled anesthesia pump (PCA) and pain scores on visual analog scale (VAS). The VAS will be measured while the patient is at rest (VAS-R) and after the patient is asked to cough (VAS-C). For each patient, the area under the curve (AUC) of the VAS-R will be calculated. Morphine usage will be tracked by patient controlled analgesia (PCA) dispensed. Using the medication chart, any rescue medications beyond the PCA will also be recorded. Patients will be interviewed and asked to rate their postoperative pain on a 10-point scale with 0 being no pain and 10 being the most pain. Another variables recorded will include incidents of nausea or vomiting, time to first ambulation, and time to first liquid and solid oral intake. All measurements for variables were obtained at 6 hrs, 12 hrs, 24 hrs, 48 hrs, 72 hrs. Nursing staff on our designated breast reconstruction floor will be instructed on how to interview patients and collect data for the 6 and 12 hour timepoints. This information will be stored on Epic EMR in a stardard note and nurses will be given a smart text to use in order to appropriately ascertain all information. The 24, 48, and 72 hour time points will be collected by the co-investigators. Any pain medications given by PCA, IV or PO will recorded and converted to morphine as diagramed below:

Drug	Parenteral (mg)	Oral (mg)
Morphine	10	30
Hydromorphone	1.5	7.5
Oxycodone	NA	20
Hydrocodone	NA	30-45
Oxymorphone	1	10
Meperidine	75	300
Codeine	130	200

Equianalgesic Potency Conversion TABLE A

Discuss limitations and difficulties

The limitations of our study include potential confounding pain from the mastectomy site, the subjectivity in patient perception of pain, and differences in patient threshold to request patient- controlled anesthesia and oral narcotics

Provide the tentative schedule for completion

Our schedule for the study will be 6 months continuous enrollment and experimentation from September to February, or until our groups are filled.

Data collection

The data fields will be: Birth date, sex, type of surgery, utilization of mesh, number of mg on PCA, VAS at rest and VAS with cough, number of rescue pain medications given, number of incidents of nausea/vomiting, time to first ambulation, time to first liquid and solid intake post surgery.

Planned Data Analysis

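### Masking is not addressed for the two injection arms, so women in Groups 1 and 3 can learn their arm, and both primary endpoints can move with that knowledge

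*Combined protocol and SAP*

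**What the plan says.** Project Design and Protocol describes blocked, stratified randomization to three named groups in equal numbers. Neither that section nor any other says who is kept unaware of the assignment. The term double-blind occurs only in titles in the reference list. The Consent section says only that consent is signed at a preoperative visit.

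On the two injection arms:
- Pre-operative Protocol: "Anesthesia will be given according to Table 1", and that table lists general anesthesia.
- Operative Technique, Group 3: "The infiltration technique for the Maracine will be identical to the EXPERAL injection".
- Figure 3 legend: one picture serves for "marking site of injection of either DepoBupivicaine or 0.25 % Bupivicaine".
- Operative Technique: every arm has two closed-suction drains; only Group 2 has infusion catheters.

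On the outcomes, all in Post-operative Protocol unless stated:
- "Our primary endpoints will be postoperative pain as measured by total postoperative morphine or hydromorphone utilization from a patient controlled anesthesia pump (PCA"), together with VAS pain scores, so there are two primary endpoints.
- Opioid is delivered through a "patient-controlled analgesia pump programmed for demand-only mode (no basal rate").
- Floor nurses collect the 6 and 12 hour data; co-investigators collect the 24, 48 and 72 hour data.
- Discuss limitations and difficulties names "differences in patient threshold to request patient- controlled anesthesia and oral narcotics" and the subjectivity of pain perception. It does not mention expectation or knowledge of the arm.

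**The concern.** With no basal rate, every PCA dose starts with the woman's own press, and VAS is her own report. Randomization balances how readily women ask for opioid at baseline. It gives no protection if that readiness changes after allocation because a woman knows what she received.

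The Rationale itself presents ordinary infiltration as short-lived and the depot product as prolonged. If women hear the same contrast, those told they had the depot product may wait longer or score lower, and those told they had the standard injection may do the opposite. Both shifts favor DepoFoam over control without any drug effect, and no analysis can remove them once the data are collected.

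The gap matters here because these two arms look alike to the woman and to the ward unless someone, or the chart, reveals the difference.

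**Working it through.** **Step 1. Can the arms be told apart after surgery?**

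| Feature | Group 1 | Group 3 | Group 2 |
|---|---|---|---|
| State when the local anesthetic is placed or injected | general anesthesia | general anesthesia | general anesthesia |
| Technique | needle infiltration | described as identical to Group 1 | two catheters |
| Drains | two | two | two |
| Infusion device after surgery | none | none | visible pump |
| PCA | demand-only | demand-only | demand-only |

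Nothing planned for the ward separates Group 1 from Group 3. Group 2 is evident on sight.

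The surgeon does know the product, and volumes may differ in the operating room. Group 1 is diluted "for a total volume of 80 cc" in Operative Technique, but the earlier dosing paragraph gives a different amount and a 60 mL dilution. For Group 3 the text gives "Thus, a 80 kg patient will be given 80 cc of 0.25% Bupivacaine", whereas 2 mg/kg × 80 kg = 160 mg, and 160 mg ÷ 2.5 mg/mL = 64 mL. These passages contradict each other and must be reconciled in any case. Masking the woman and the ward does not depend on matched syringes, because neither sees them.

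**Step 2. Illustration of size.** The plan gives no expectation effect, sample size, alpha or power, so there is no plan figure to reproduce.

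From Sample Size Justification: difference 5 and SD 4.9 for total day-3 morphine (unit taken as mg); difference 0.7 and SD 0.7 for VAS.

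Assumed:
- True drug effect zero; two-sided 5% two-sample t-test of Group 1 versus Group 3.
- Expectation shift b of 0.5, 1.25 or 2.5 mg (a tenth, a quarter and a half of 5). For VAS, 0.175 or 0.35 (a quarter and a half of 0.7).
- n = 17 per group, close to the 16 that the plan's inputs imply at an assumed 80% power: 2 × (1.96 + 0.84)² × 4.9² ÷ 5² ≈ 15.1, rounded up to 16.
- n = 10 per group, about what six months would yield from the stated annual volumes if every woman enrolled: 54 ÷ 2 ÷ 3 = 9 and 66 ÷ 2 ÷ 3 = 11.

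Formula: SE = SD × √(2/n); noncentrality δ = b ÷ SE; rejection rate = P(|T| > critical t), with T noncentral t on 2n − 2 degrees of freedom.

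Morphine SE is 4.9 × √(2/17) = 1.68 at n = 17 (critical t 2.037) and 4.9 × √(2/10) = 2.19 at n = 10 (critical t 2.101).

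| Morphine shift | δ, n = 17 | Rejects | δ, n = 10 | Rejects |
|---|---|---|---|---|
| 0 | 0 | 5% | 0 | 5% |
| 0.5 mg | 0.30 | 6.0% | 0.23 | 5.5% |
| 1.25 mg | 0.74 | 11% | 0.57 | 8% |
| 2.5 mg | 1.49 | 30% | 1.14 | 19% |

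For VAS at n = 17, SE = 0.7 × √(2/17) = 0.240. A shift of 0.175 gives δ = 0.73 and rejection in 11%; 0.35 gives δ = 1.46 and 29%.

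**The case against.** **Silence is not an open design.** A reader might infer that the comparison is run open by decision, or that women are told their arm. The documents say neither, and the consent form was not available for this review. This stands: women can learn their arm; it is not established that they will. Silence still leaves disclosure to individual staff.

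**The size is assumed throughout.** The shift, the group sizes and the pairwise test are not in the plan, which specifies a three-group repeated-measures ANOVA and, if the interaction is significant, an ANOVA at 72 hours. At a 0.5 mg shift the error rate stays near 5%. This stands, so the figures cannot establish how serious the bias is.

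**Day-3 morphine is not PCA presses alone.** Oral narcotics typically start on postoperative day 1, and PCA, IV and oral doses are all converted to morphine. This stands. Oral requests can also respond to expectation, and the plan's own limitation names them. A reader might go further and infer that nurses would offer oral narcotics sooner to control patients; the plan ties the offer to diet, not to arm, so that route is not supported.

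**The main question is pump versus DepoFoam.** The stated purpose is that comparison, and masking Groups 1 and 3 does not protect it. This also stands, but the first aim includes the control cohort, and the Significance section asks whether either method improves on standard analgesia.

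**Hiding a drug's identity on the ward has a cost.** This is fair: pharmacy handling and chart set-up for the study injection are not described, and immediate access to the product identity is needed.

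**Conclusion.** The point holds as a gap that is cheap to close. No masking is stated for patients, floor nurses or data collectors; both primary endpoints depend on the woman's behavior or report; and the DepoFoam and control arms can be kept indistinguishable to her and to the ward. Knowledge of the arm could therefore bias that one contrast.

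Three stronger readings go too far. PCA use is not the only primary endpoint; VAS is equally exposed. The 11% and 30% figures do not estimate this trial's false-positive rate: they show only what shifts of a quarter and a half of the planned difference would do, and a tenth leaves the rate at about 6%. Finally, the masking possible here does not reach the operating surgeon or either comparison with the pump.

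The conclusion rests on the absence of masking text and the similarity of the two injection arms, not on the illustration.

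**What to change.** Add to Project Design and Protocol, to Post-operative Protocol and to the consent form:

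1. Women in Groups 1 and 3, the floor nurses who collect the 6 and 12 hour data, and the co-investigators who collect the 24, 48 and 72 hour data are not told which injection was given until the 72-hour reading is complete.
2. The operating surgeon and anyone else who knows the arm neither disclose it nor collect these readings. The co-investigators matter particularly because the 72-hour point becomes the primary focus if the interaction is significant.
3. The floor chart carries a neutral label, such as study local anesthetic injection. The product identity stays in the anesthesia record, available at once for clinical need.
4. Group 2 is open, and the masked claim is limited to DepoFoam versus control.

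The cost is wording in the protocol, consent form and chart label, plus a route for immediate unmasking. Any co-investigator who knows the arm, for example from the operating room, would have to be replaced as data collector. It needs no sham pump and no change in sample size. The pump comparisons stay open, and reports should say so.

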Comparison of Local Anesthetic Infusion Pump Versus Depofoam Bupivacaine for Pain Managemen

Date 12/12/2015 ID: 15-1535

Purpose

We propose a randomized controlled study to compare the effectiveness of a localanesthetic continuous infusion pump system versus locally injectable FDA approved DepoFoam bupivacaine (Experal) for postsurgical analgesia in patients undergoing unilateral DIEP free flap reconstruction.

Specific Aims

- Compare the amount of postoperative narcotic use in patients with a localanesthetic continuous infusion pump system, locally injectable liposomal bupivacaine, and a control cohort by recording the type and amount of narcotic use from a patient's medication records.
- 2) Examine the incidence of narcotic-related side effects in the experimental groups as compared to the control cohort by documenting incidents of nausea and vomiting, time to first ambulation, and time to first liquid and solid oral intake.
- 3) Survey patient satisfaction with pain management using a visual analog scale during their hospital stay.

Rationale for the Project

Effective post-surgical pain control in patients undergoing unilateral deep inferior epigastric perforator (DIEP) free flap reconstruction. is critical to patient recovery, and can contribute to faster patient mobilization, shorter hosital stays and reduced health care costs. The admisitration of local anesthetics via wound infiltration is standard of care and an effective practice for postsurgical pain management. However, this method only provides relatively brief analgesia, usually lasting only 12 hours. Other FDA approved delivery systems using an indwelling fusion pump catherter (On–Q pump) are currently being used in our practice and may be used to extend the duration of action of locally adminisisted analgesia by continously infusing anesthetic into the wound. Alternativley, a depot form of bupivicaine has been FDA approved and currently used to deliver a single-dose admistered via wound infiltration for prolonged analgesia by allowing for the diffusion of the drug over an extended period of time. Both of these products are used as standard practice during DIEP free flap reconstructions. However, no studies compare the efficacy of these two methods patients undergoing unilateral DIEP flap reconstructions has been done in a prospective, randomized control manner.

Significance

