The data will be examined with an analysis of variance (ANOVA) procedure with repeated measures. The design will have one between factor, (group (3), and one within factor, time (6). The analysis will test for a group effect, a time effect and a group by time interaction. We anticipate that the three groups will be comparable at the start. This implies the likelihood of a significant interaction term. If this happens, our primary analysis will focus on the ANOVA for the 72-hour time point. This will show us if a differential effect has occurred. All assumptions of the test will be examined and data transformations or nonparametric methods used if indicated.

We will not be utilizing QHS, rather, one of the plastic surgery residents, [name], will serve as our statistician.

Sample Size Justification

We propose to randomly assign individuals recruited during the recruitment period into 3 equal groups. With three groups this translates to a difference between groups of 5 for total morphine used on day 3 and 0.7 for the VAS. This assumes standard deviations of 4.9 for morphine and 0.7 for VAS. Effects of these sizes represent clinically important differences in the range that we believe will happen.

References:

- Feng LJ. Painless abdominoplasty: the efficacy of combined intercostal and pararectus blocks in reducing postoperative pain and recovery time. Plast Reconstr Surg. 2010 Nov;126(5):1723-32.

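### The PCA-only primary opioid endpoint does not measure Aim 1, and its window differs between the endpoint text (total postoperative) and the sizing and analysis text (day 3, 72 h)

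*Combined protocol and SAP*

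**What the plan says.** **Route.** The Post-operative Protocol section names two primary measures, opioid use and VAS pain. For opioid use it says "Our primary endpoints will be postoperative pain as measured by total postoperative morphine or hydromorphone utilization from a patient controlled anesthesia pump (PCA", and adds "Morphine usage will be tracked by patient controlled analgesia (PCA) dispensed". Rescue drugs outside the PCA are noted as well. Later in the same section comes "Any pain medications given by PCA, IV or PO will recorded and converted to morphine as diagramed below", which points to Table A. No sentence assigns that converted total to an endpoint.

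Aim 1 (Specific Aims) compares narcotic use across the three groups by "recording the type and amount of narcotic use" from the medication records, with no restriction to the PCA. The Post-operative Protocol makes oral narcotics available once diet is advanced, usually on day 1. The Data collection list has milligrams for the PCA but only a number for rescue medications.

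**Window.** The endpoint text gives no end time. Sample Size Justification works with "a difference between groups of 5 for total morphine used on day 3" and then says "This assumes standard deviations of 4.9 for morphine and 0.7 for VAS". The 5 has no unit; the 4.9 has no unit, day or route. Planned Data Analysis begins with a repeated-measures ANOVA. If the group-by-time interaction is significant, "our primary analysis will focus on the ANOVA for the 72-hour time point".

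**The concern.** Two things are at stake.

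- **Route.** The declared variable answers a narrower question than Aim 1. A patient who moves from the PCA to tablets appears to use less opioid although total use may be unchanged. If that move happens at different rates or times in the three arms, a PCA-only comparison mixes opioid sparing with switching of route.
- **Window.** A total over the whole postoperative period and an amount on day 3 are different quantities, with different expected differences and SDs. The plan declares one, sizes on the other, and lets an interaction test decide whether the 72-hour analysis becomes primary. Two analysts following the text could report different primary opioid results.

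**Working it through.** The plan states no sample size, alpha or power, so it has no figure of its own to reproduce. The checks below use only its stated inputs.

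**1. How much of the period is affected by route.** Assume oral narcotics start at about 24 h (the plan says typically day 1). Then 72 − 24 = 48 of the 72 hours, two thirds, fall after that start. Day 3, read as 48–72 h, falls in it entirely.

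**2. What a tablet is worth on the morphine scale.** Table A equates 20 mg oral oxycodone with 10 mg parenteral and 30 mg oral morphine.
- 10 mg oxycodone = 10 × 10/20 = 5 mg parenteral morphine, the same number as the design difference of 5.
- On the oral scale it is 10 × 30/20 = 15 mg. The plan does not say which scale is meant.
- Hydrocodone has a range, 30–45 mg, so 20 mg converts to anything from 20 × 10/45 = 4.4 to 20 × 10/30 = 6.7 mg parenteral morphine.

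The documents give no oral doses by arm, so this shows only the scale on which omitted tablets count.

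**3. Whether the pilot values are running totals** (Significance section; 30 min, 6, 12, 24, 48, 72 h).
- Exparel: 5.2, 6.2, 5.5, 5.98, 5.23, 2.7 mg.
- On-Q: 1.2, 16.42, 14.8, 14.9, 11.63, 12.65 mg.

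Both series go up and down. A running total in the same patients cannot fall, so these are not cumulative amounts. That does not prove that they are adjoining intervals; step 4 assumes it.

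**4. Size of the window difference under that assumption.**
- 72 h gap: 12.65 − 2.7 = 9.95 mg.
- Six values: On-Q 71.60, Exparel 30.81, gap 40.79 mg; 9.95/40.79 = 24%.
- This trial's five times (without 30 min): 70.40 − 25.61 = 44.79 mg; 9.95/44.79 = 22%.

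The two windows differ by a factor of 40.79/9.95 = 4.1 to 44.79/9.95 = 4.5.

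**5. Whether an SD of 4.9 carries over.** Assume that each of five intervals has SD 4.9, with common correlation ρ. The SD of the sum is 4.9 × √[5(1 + 4ρ)], which is 11.0 at ρ = 0 and 24.5 at ρ = 1. A difference and SD chosen for one window therefore do not serve the other.

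**6. Effect of a changed SD.** For fixed n, alpha and power the detectable difference is proportional to the SD. If the all-route SD were 6 or 7 (assumed values) instead of 4.9, it would rise by 6/4.9 = 1.22 or 7/4.9 = 1.43.

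**The case against.** The strongest defence is that the plan does choose. The endpoint sentence names the PCA, the tracking sentence repeats it, and the data field is PCA milligrams. Other drugs are only recorded alongside, and a conversion table is needed anyway because the PCA may hold hydromorphone. This stands: a reader might infer that the plan never says which route is primary, and that would be wrong. What remains is that the chosen route does not match Aim 1, and that converting IV and oral drugs serves no stated purpose.

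On the window, day 3 and the 72-hour time point can mean the same interval, and sizing a repeated-measures endpoint on one time point is not in itself a contradiction. That also stands. The conflict is between those two and an open-ended total. The repeated-measures model does not settle it: it has "one within factor, time (6", that is six levels where the endpoint text lists five times, and the plan does not say whether each value is an interval amount or a running total.

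A reader might also infer that PCA-only counting will produce false positive results at some rate, or will favour Exparel because that arm ate earlier in the pilot. The documents support neither. They give no oral doses by arm, and the earlier eating is unquantified and may no longer matter by day 3. The pilot had 15 and 5 patients, reports no SDs, and describes its comparator in two different ways.

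**Conclusion.** The concern holds as a mismatch between endpoint and aim, together with an inconsistent window. The PCA-only total leaves out part of the opioid use that Aim 1 asks about, over roughly two thirds of 72 hours if oral drugs start near 24 h. The resulting distortion has unknown size and direction. The window changes the pilot contrast about four-fold, provided that the pilot values are adjoining interval amounts.

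Two further inferences are not supported. One is that an all-route day-3 variable is what the study was sized for: the sizing names day 3 for the difference, but gives no route for it and neither route nor day for the SD, so at most the window agrees. The other is that the trial is underpowered: no sample size, alpha or power is stated. Choosing between day 3 and 0–72 h is the sponsor's decision; leaving both in place is the defect.

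**What to change.** - **Variable.** Make the primary opioid variable the all-route total (PCA + IV + PO) in parenteral-morphine mg by Table A. Fix one hydrocodone factor before data are seen. Report PCA-only use as secondary.
- **Data.** Record drug, route, mg and time from the medication chart in place of a count of rescue medications.
- **Window.** State one window and use it in Specific Aims, the endpoint text, Planned Data Analysis and Sample Size Justification. Either keep day 3 (48–72 h), which the sizing names, with the 0–72 h total as secondary; or make 0–72 h primary and re-derive both the difference and the SD.
- **Test.** Analyse that variable, one value per patient, by a three-group one-way ANOVA whether or not the interaction is significant. The repeated-measures ANOVA can stay as supportive.

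**Cost.** Wording changes and a little more abstraction; the doses are already in the medication chart. The all-route SD may differ from 4.9, so it must be rechecked and the detectable difference restated. If day 3 is kept, it covers only 22–24% of the pilot's summed gap on the interval reading, which is why the 0–72 h secondary is needed. With either window, a rule is needed for patients discharged before 72 h, whose amounts are incomplete.

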A total of twenty patients were randomized into Depofoam bupivacaine group (Exparel, n=15), and continuous infusion pump system (On-Q, n=5) after undergoing abdominoplasty or TRAM flaps. The Exparel group demonstrated higher morphine usage at the 30 minute time point compared to the On-Q group (5.2 mg vs 1.2mg), but a significantly lower volume at all other time points when compared to the On-Q group (6.2 mg vs 16.42 mg at 6 hrs; 5.5 mg vs 14.8 mg at 12 hrs; 5.98 mg vs 14.9 mg at 24 hrs; 5.23 mg vs 11.63 mg at 48 hrs; 2.7 mg vs 12.65 mg at 72 hrs). The VAS scores for the On-Q group were higher at the earlier time points (up to 6 hours) when compared to Exparel group and relatively the same during the remainder of the study (Figure 1 and Figure 2). The remaining variables that were examined revealed that the Exparel group had more nausea and vomiting at earlier time points but that the same group was ambulating, drinking and eating solid food at earlier time points than the On-Q group.

From this pilot study we concluded that with the use of a depot form of bupivicaine (Exparel), more effective postsurgical pain control was achieved in patients undergoing abdominoplasty or TRAM flap reconstruction than those that used an indwelling fusion pump catherters (On–Q pump). Further studies are necessary to enroll more participants undergoing these specific procedures in which this type of post surgical pain control may be most effective.

Our goal in this study is to expand the finding based from our pilot study by observing only those that undergo breast reconstruction with a DIEP flap.

[figure not shown]
[figure not shown]

Figure 2

Subjects in the project

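### Pain interviews pass from nurses to co-investigators at 24 h with no masking stated, so any arm-specific interviewer effect would look like the interaction that makes the 72-hour ANOVA primary

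*Combined protocol and SAP*

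**What the plan says.** The Post-operative Protocol makes PCA opioid use and VAS pain, at rest and on coughing, the primary endpoints. On how pain is obtained it says "Patients will be interviewed and asked to rate their postoperative pain on a 10-point scale". The schedule has five times: "All measurements for variables were obtained at 6 hrs, 12 hrs, 24 hrs, 48 hrs, 72 hrs".

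The assessor differs by time. Nursing staff on the breast reconstruction floor "will be instructed on how to interview patients and collect data for the 6 and 12 hour timepoints", and they record in a standard note with a smart text. Then "The 24, 48, and 72 hour time points will be collected by the co-investigators". No instruction or template is described for the co-investigators.

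The Planned Data Analysis is a repeated-measures ANOVA with group, time and their interaction. It expects a significant interaction and says that in that case "our primary analysis will focus on the ANOVA for the 72-hour time point".

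No section says that patients, nurses, co-investigators or the analyst are masked; the term double-blind occurs only in the titles of cited studies. Under Operative Technique, Group 2 has two indwelling catheters and a pump, and no sham is described for the other groups. The listed limitations include the subjectivity of pain, but neither the change of assessor nor masking.

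**The concern.** A pain score given in an interview can be influenced by who asks and what they expect. Here the interviewer changes between 12 and 24 h, and the second set of interviewers supplies every later reading, including the 72-hour one.

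An interviewer effect confined to one arm would be absent at 6 and 12 h and present at 24, 48 and 72 h. That pattern is a group-by-time interaction, which the plan already expects and would read as a treatment effect. The plan's rule then sends the primary analysis to the 72-hour ANOVA, which carries the same bias. Once the data are in, such an effect cannot be separated from a real late difference between arms.

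The exposure is limited to VAS and the other interview items. Pump milligrams and charted drugs do not depend on the interviewer in the same way.

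**Working it through.** **Inputs from the plan.** Three equal groups (Project Design and Protocol). Five measurement times (Post-operative Protocol); the analysis section gives the time factor six levels, and five are used here because five are listed. VAS SD 0.7 and target difference 0.7 (Sample Size Justification).

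**Assumed, because the plan does not give them.** Two-sided alpha 0.05; 15 or 20 patients per group; within-patient correlation ρ = 0.5 at all pairs of times; no true treatment effect; a shift δ in one arm at 24, 48 and 72 h of 0.2, 0.35 (half the planned difference) or 0.5. The plan has no sample size, power or false-positive figure to reproduce. As a guide to n, a pairwise comparison with difference 0.7 and SD 0.7 needs 2 × (1.960 + 0.842)² × (0.7/0.7)² = 15.7, so 16 per group for 80% power, and 2 × (1.960 + 1.282)² = 21.02, so 22 for 90%.

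**Step 1: a shift common to all arms.** Adding 0.7 points to every arm from 24 h on leaves the interaction test at about 5%, the 72-hour ANOVA at about 5%, and both together under 1%. The time effect absorbs it.

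**Step 2: a one-arm shift, 72-hour ANOVA.** The noncentrality is λ = n × (2/3) × δ²/SD². At n = 20 and δ = 0.35, λ = 20 × 0.667 × 0.1225/0.49 = 3.33 on 2 and 57 df, giving 34% rejection.

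**Step 3: the same shift, interaction test.** After removing group and time means, the shift pattern has sum of squares (2/3) × (3 × 2/5) × δ² = 0.8δ². So λ = n × 0.8δ²/[SD²(1 − ρ)]. At n = 20 and δ = 0.35, λ = 20 × 0.8 × 0.1225/(0.49 × 0.5) = 8.0 on 8 and 228 df, giving 46%.

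**Step 4: both together.** The plan reaches the 72-hour ANOVA through a significant interaction, so the joint rate is the relevant one. It was simulated.

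| n per group | δ | Interaction | 72-hour ANOVA | Both |
|---|---|---|---|---|
| 20 | 0 | 5% | 5% | under 1% |
| 20 | 0.2 | 16% | 14% | 4% |
| 20 | 0.35 | 46% | 34% | 19% |
| 20 | 0.5 | 82% | 62% | 53% |
| 15 | 0.2 | 12% | 11% | 3% |
| 15 | 0.35 | 34% | 26% | 12% |
| 15 | 0.5 | 67% | 48% | 35% |

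Repeat simulations move the joint figures by a point or so (18% to 20% and 52% to 54% for the two larger shifts at 20 per group). Correlation matters: at n = 20 and δ = 0.35 the joint rate is about 15% at ρ = 0.3 and 26% at ρ = 0.7.

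**Step 5: one unmasked assessor type throughout.** If the 0.35 shift is present at all five times, the interaction test returns to 5%, but the 72-hour ANOVA still rejects in about 34% of trials at 20 per group, since λ in Step 2 is unchanged. Uniform assessors remove the artificial interaction, not the bias at 72 h.

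**The case against.** **The hand-over is harmless in itself.** This is right for any effect shared by all arms, as Step 1 shows. A reader might infer that changing interviewers already biases the comparison of arms; it does not. Only an effect that differs by arm matters.

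**Knowledge of the arm is not established.** The documents do not say that the co-investigators know the allocation or that they operate. The infiltration in Groups 1 and 3 is described as the same technique, so at the bedside only Group 2 is recognisable, and nurses would recognise it too. This stands. The point is that nothing in the plan prevents knowledge of the arm.

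**The pilot supplies little motive.** The Significance section concludes that with the depot form "more effective postsurgical pain control was achieved in patients undergoing abdominoplasty or TRAM flap reconstruction", compared with the pump. A reader might take this as evidence that late VAS scores will be shaded. But the pilot's VAS scores differed only up to about 6 h and were similar afterwards; the later differences were in morphine. The stated preference is a reason for care, not evidence of bias at 24 to 72 h.

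**The single-test rates overstate the problem.** A reader might take the 14%, 34% and 62% for the 72-hour ANOVA at 20 per group as the rate at which interviewer effects both trigger and decide the primary analysis. That calls for the joint rates of 4%, 19% and 53%. At a shift of 0.2 the joint rate is below 5%, though still several times the rate with no shift.

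**The rule is conditional, and opioid use is also primary.** Both are true. The 72-hour ANOVA becomes primary only if the interaction is significant, though the plan expects that. The point does not reach the PCA endpoint to any comparable degree.

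**Conclusion.** The concern holds as a design weakness in one of the two primary endpoints. The hand-over at 24 h and the conditional 72-hour rule are stated, and masking is nowhere mentioned. Together they allow an arm-specific interviewer effect to produce a significant interaction and bias the analysis that follows from it.

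The size depends on assumptions that the documents cannot settle. A shift of half the planned VAS difference would give the two-step false result in about 12% to 19% of trials at 15 to 20 per group and correlation 0.5, instead of under 1%. A shift of 0.2 would give about 3% to 4%.

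The documents do not support saying that bias will occur, that the co-investigators are unmasked to the two injection arms, or that the opioid results are compromised. It is worth changing because the remedy is cheap and must be in place before enrolment.

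**What to change.** - Have the patient mark VAS-R and VAS-C herself at all five times, using one scripted procedure and the same smart text, with the scale handed out by the same floor nurses.
- Limit co-investigators to pump-log and chart data.
- Give the analyst groups coded A/B/C until the primary analysis is final.
- List the remaining lack of masking as a limitation.

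The cost is three more short entries per patient (24, 48 and 72 h) for nurses already on the floor and already to be instructed, plus someone other than the analyst to hold the group code. No treatment or procedure changes. Keeping the injected drug from floor staff is not proposed, because it touches clinical care.

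The fix is partial. It removes the change of assessor, and self-marking reduces the interviewer's influence. The pump remains visible and patients may know their arm, so some bias at 72 h can remain.
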